TITLE: Ultrasound guided posterior quadratus lumborum block for improved postoperative analgesia in minimally invasive gynecologic surgery

Date: June 19, 2020

TITLE

Ultrasound guided posterior quadratus lumborum block for improved postoperative analgesia in minimally invasive gynecologic surgery

INTRODUCTION

The overall decrease in morbidity associated with advances in minimally invasive surgery has transformed the concept of postoperative management, with lower complication rates, earlier mobilization, rapid postoperative recovery, and earlier discharge from the hospital. However, at times, laparoscopic surgery is associated with higher postoperative pain than traditional laparotomy in the immediate postoperative period; often requiring significantly higher doses of pain medication within the first 4 hours after surgery. In general, laparoscopic procedures could be associated with longer operative times; however, minimally invasive surgeons are presented with the most challenging patients- often morbidly obese, prior history of several surgical procedures in the abdomen and pelvis, and/or adhesive disease. Overall operative time is increased, including time under general anesthesia and amount of surgical dissection, which makes control of postoperative pain all the more problematic.

BACKGROUND AND SIGNIFICANCE

The challenge to achieve adequate analgesia has led to the development of directed, multi-modal protocols specific to management of post-laparoscopy pain in effort to decrease the amount of additional administration of narcotic medication. While several non-opioid regimens have been found to be effective, opioid medications still play a significant role in early postoperative analgesia. Given the adverse side effects of narcotic medications, regional blocks utilizing local anesthetic agents and has been shown to improve overall pain control in this time period.

Truncal abdominal nerve blocks are useful for pain control in abdominal and pelvic surgeries. More recently, the utilization of the quadratus lumborum (QL) block has effectively alleviated somatic and visceral pain in the upper and lower abdomen. The QL block provides analgesia spanning from the T4 to L1 dermatomal levels in the thoracolumbar plane to provide a broad sensory level analgesic effect. The approach involves injecting local anesthetic under ultrasound guidance into the plane posterior to the quadratus lumborum muscle and middle layer of thoracolumbar fascia.

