Given the utility of the QL block in controlling somatic pain, this study aims to determine whether the QL block is an effective analgesic adjunct in the control of postoperative pain period, specifically with regards to patients undergoing laparoscopic gynecologic surgery.

STUDY OBJECTIVES

this study aims to determine whether the posterior QL blocks is an effective analgesic adjunct in the control of postoperative pain period, specifically with regards to patients undergoing laparoscopic gynecologic surgery.

HYPOTHESIS

The patients receiving QL blocks will have lower post-operative pain scores and will need less oral supplemental pain killers.

Subjects:

Women aged 18 to 65 presenting for scheduled laparoscopic or robotic total or supracervical hysterectomy for benign indication.

Eligibility Criteria:

Patient will be eligible for recruitment if between the ages of 18 to 65 scheduled to undergo laparoscopic or robotic total or supracervical hysterectomy for benign indications. Only surgery for benign pathology will be considered to enrollment. No Malignancy cases will be included.

Exclusion criteria:

1. History of adverse reaction or allergy to Bupivacaine or liposomal bupivacaine
2. Medical contraindication to placement of QL block.
3. Suspicion of possible reproductive cancer with contraindication of morcellation of uterine tissue.
4. Significant medical condition or laboratory result that in the opinion of the Investigator indicate an increased vulnerability to study subject which exposes the subject to an unreasonable risk as a result of participating.
5. Any clinically significant condition uncovered during the surgery, such as excessive bleeding or decompensation, that might render the subject medically unstable to continue the study or complicate the subject's intraoperative or postoperative course.

6. Pregnant patients
7. Less than 40Kg weight.

Design:

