Prospective Cohort observational study. All patients that meet criteria for participation in this study will be screened: patients scheduled to undergo a laparoscopic hysterectomy for benign conditions by attending physicians in the division of Minimally Invasive Gynecologic Surgery. Based on surgeon's preference, and patient's consent, the patient is offered a QL block or not. Our aim is to follow the patient's pain scores post op and amount of oral pain medication used whether they received QL block or not. If the patient received the QL block then they will be considered part of the study arm. If the patient did not receive the QL block then they will be considered part of the control arm.

The QL block is best thought of as a volume or compartment block in that volumetric spread of LA along the fascial plane is associated with efficacy in blocking the thoracolumbar nerves between T7-L1. It can be reasonably assumed that this compartment is the same across patients and is not affected by the amount of subcutaneous or central fat present in the obese patient.

If a block is to be performed, the QL block will be performed using a 21G x 100mm Stimuplex needle under ultrasound guidance using a curvilinear probe. Subjects will be positioned in the semi-lateral position to facilitate access into the plane posterior to the quadratus lumborum muscle and middle layer of thoracolumbar fascia. The QL block will be administered via an in-plane approach and local anesthetic will be injected between the quadratus lumborum muscle and the middle layer of the thoracolumbar. The QL block will be in the operating room after induction prior to starting the scheduled surgical procedure. If the block is performed, it will include 20ml of 0.25% bupivacaine and 5ml of liposomal bupivacaine (Exparel) per side. The block will be done bilaterally therefore **a total** of 40ml of 0.25% bupivacaine and 10ml of liposomal bupivacaine (Exparel) will be administered.

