Patients will be pre-medicated with Midazolam. Routine monitoring will be performed including electro-cardiography, non-invasive blood pressure monitoring, heart rate oxygen saturation and end-tidal carbon dioxide and capnograph will be performed. General anesthesia will be induced with Propofol 1-2 mg/kg and analgesia will be provided with Fentanyl 2 mcg/kg. General anesthesia will be maintained using the Sevoflurane titrated to effect as determined by the anesthesia team caring for the patient. Rocuronium will be administered during the duration of the case to provide muscle relaxation for the duration of the procedure, with an induction dose of 0.6 mg/kg and titrated to 1-2 twitches assessed by continuous twitch monitor. Reversal of neuromuscular blockade will be achieved using 0.06 mg/kg of Neostigmine and 0.012mg/kg of Glycopyrrolate or 2mg/kg of sugammadex.

Possible allergic type reactions of receiving bupivacaine include urticaria, pruritis, erythema, angioedema, tachycardia, sneezing, nausea, vomiting, dizziness, and syncope. Overdosage or rapid absorption lead to systemic toxicity manifestation that need immediate counter measures related to the central nervous system and cardiovascular system. There is also risk of nerve injury given the location of the regional block. Routine precaution is taken by the surgical and anesthesia team to avoid overdosing. Any reactions or overdosing will be managed accordingly. The study will not alter the subjection to possible adverse reaction as this is an observational study.

Data Collection Procedures:

As this is an observational (prospective cohort) study, there will be no randomization or blinding done. We will be observing the patient's post op pain scores and amount of pain medication used

Postoperatively, patients will be transferred to the PACU for monitoring. The amount, timing and type of additional pain medications necessary at 1 and 3 hours after surgery will be recorded. Pain levels will be documented at the same 1- and 3-hours intervals, and scored utilizing a 1-10 Numeric Rating Scale (NRS). The NRS is a verbal assessment, asking patients to quantify their pain on 1- 10 scale. It has previously been shown in studies to be a simple, valid alternative to the visual analog scale (VAS).

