Study subjects will receive a telephone call 24 hours after surgery and asked about how much additional medication they have taken for pain control, as well as their pain level utilizing the same 1-10 NRS assessment.

Our primary outcome is difference in pain scores at 3 hours. Our secondary outcome is difference in pain scores, at 1 hour, 24 hours, difference in additional medication taken orally for pain control, and adverse effects if any.

Sociodemographic and clinical data of study subjects will also be obtained, including age, body mass index, history of abdominal and pelvic surgeries, history of pelvic adhesive diseases such as endometriosis, duration of surgery, and duration of stay postoperatively in PACU.

Data Analysis: the mean difference between pain scores at 1 hour, 3 hour, and 24 hour, and the difference in the amount of oral pain medication used will be assessed as below.

Expected Outcomes: Our study aims to show that patients receiving a preoperative QL block will have lower post-operative pain scores and will need less oral pain medication

REFERENCES:

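### Extent of surgery, which the protocol itself links to postoperative pain, is captured only through proxies, and no adjusted analysis is stated, so confounding by extent would remain in the 3-hour comparison

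*Combined protocol and SAP*

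**What the plan says.** The Introduction describes the patients referred for minimally invasive surgery as "often morbidly obese, prior history of several surgical procedures in the abdomen and pelvis, and/or adhesive disease". It then says that operative time is longer, "including time under general anesthesia and amount of surgical dissection, which makes control of postoperative pain all the more problematic".

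The arms are formed by choice. Under Design: "Based on surgeon's preference, and patient's consent, the patient is offered a QL block or not". Data Collection Procedures confirms that "there will be no randomization or blinding done". When a block is given, Design places it "in the operating room after induction prior to starting the scheduled surgical procedure".

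The Subjects section admits women presenting for "scheduled laparoscopic or robotic total or supracervical hysterectomy for benign indication", so two routes and two types of hysterectomy are eligible.

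The data list in Data Collection Procedures is open-ended. It names age, body mass index, "history of abdominal and pelvic surgeries, history of pelvic adhesive diseases such as endometriosis, duration of surgery" and length of PACU stay. The primary outcome is the difference in pain score at 3 hours. The Data Analysis paragraph promises mean differences assessed by a method described below it, but no method follows and no covariate adjustment is mentioned.

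**The concern.** In a non-randomized comparison, a factor that affects pain and also influences who gets the block will shift the difference between arms. The protocol supplies both halves of that condition. It says that dissection affects pain, and it lets surgeons, who know the planned operation and the patient's history, steer the choice. A surgeon who expects a difficult operation may be more inclined to want the block, or less. The first would hide a benefit and the second would exaggerate it.

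The listed items describe what the patient brought to surgery and how long it took, not what was done. A history of endometriosis does not show whether disease was found or excised. Duration mixes extent with surgeon speed and route. Nothing listed records adhesiolysis, excision, concomitant procedures, route or hysterectomy type. At stake is whether a reader of the 3-hour result can tell a block effect from a difference in the operations performed.

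**Working it through.** The plan gives no sample size, standard deviation, target difference or expected imbalance, so there is no figure to reproduce. The check has two parts: the Introduction set against the data list, then an illustration on assumed inputs.

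**1. Factors named against items listed**

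| Factor in the Introduction or Subjects section | Item in Data Collection Procedures |
|---|---|
| Obesity | BMI |
| Prior abdominal or pelvic surgery | History of such surgery |
| Adhesive disease | History of adhesive disease |
| Operative time | Duration of surgery |
| Time under general anesthesia | Not listed; duration of surgery is a proxy |
| Amount of dissection | Not listed; duration and the histories are proxies |
| Laparoscopic or robotic | Not listed |
| Total or supracervical | Not listed |

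The three patient-level causes of difficult surgery are covered. Dissection is covered only indirectly, and route and type not at all.

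**2. When extent confounds**

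The block precedes the first incision. Extent discovered later can be associated with block choice only if it was foreseeable at that time or goes with the surgeon. Extent that meets neither condition adds noise to the pain scores but no bias. The pre-block variables (planned procedure, route, type, surgeon, history) therefore matter most.

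**3. Unadjusted shift, extent as yes/no (assumed inputs)**

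Shift = (difference between arms in the share with extensive dissection) × (added NRS points).

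- 0.10 × 0.5 = 0.05
- 0.20 × 1.0 = 0.20
- 0.30 × 1.5 = 0.45

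**4. Unadjusted shift, extent on a continuous scale (assumed inputs)**

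Shift = g × d, where g is NRS points per SD of extent and d is the imbalance between arms in SDs.

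- Low: 0.5 × 0.2 = 0.10
- High: 1.0 × 0.5 = 0.50

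Taken together, the two versions span 0.05 to 0.50 points, with the sign set by which patients surgeons select.

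**5. What adjusting for a proxy would leave**

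Remaining shift = g × d × (1 − r²), where r is the within-arm correlation between the proxy (such as duration) and extent.

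| r | Fraction left, 1 − r² | Remaining shift, low to high |
|---|---|---|
| 0.5 | 0.75 | 0.075 to 0.375 |
| 0.7 | 0.51 | 0.051 to 0.255 |
| 0.9 | 0.19 | 0.019 to 0.095 |

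A simulation with 400,000 subjects per scenario agreed with this formula to within 0.02 points. Proxies thus remove part of the bias, and a good proxy removes most of it. With no adjustment planned, even that part is not removed, and the shifts in steps 3 and 4 apply in full.

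**The case against.** A reader might infer that the plan collects nothing but patient history and operative time, so that extent cannot be separated from the block at all. The documents do not support that. Age, BMI and PACU stay are also listed, and the wording leaves the list open. The Introduction itself ties dissection to operative time, and duration is collected. The patient-level causes it names are all on the list. Partial separation is possible, as step 5 shows.

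Nor would the information necessarily be lost for good. If operative notes are kept, the items could be abstracted later. But an open-ended list commits nobody to doing so.

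Two further objections carry weight. First, surgical findings recorded after the block are not clean baseline variables. Whether a concomitant procedure is done, and how adhesiolysis is graded, depends partly on decisions and documentation during the operation. One cannot simply assert that adjusting for them is harmless, which is why they belong in a sensitivity analysis. Second, extra fields achieve little beyond description unless an adjusted analysis exists, and none is stated. The missing adjustment is the more basic gap.

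It is also fair to say that the assumed shifts are modest on a 1–10 scale. With no target difference or SD in the plan, they cannot be shown to be decisive or negligible. What survives is narrower but real: a pain driver named by the protocol, preference-based arms, indirect capture, and no adjustment.

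**Conclusion.** The point holds in this form. Extent of surgery is captured only through proxies, route and hysterectomy type are not listed, and only an unadjusted mean difference is stated. Confounding by extent would therefore remain in the primary 3-hour comparison, so far as extent was foreseeable at block choice or linked to the surgeon.

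The size cannot be derived from the documents. The range of about 0.05 to 0.5 NRS points rests wholly on assumed imbalances (10 to 30 percentage points, or 0.2 to 0.5 SD) and assumed effects on pain (0.5 to 1.5 points, or 0.5 to 1.0 point per SD). The direction is unknown. The documents do not show that surgeons select on expected extent, only that the design allows it. The change is worth making because it is cheap, but this is not evidence that the result will be wrong.

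**What to change.** Add to the list in Data Collection Procedures, taken from the booking record and operative note:

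- operating surgeon (coded);
- route (laparoscopic or robotic);
- hysterectomy type (total or supracervical);
- planned concomitant procedures;
- adhesiolysis or endometriosis excision performed (none / limited / extensive).

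Report each by arm. In Data Analysis, state that the primary 3-hour comparison is a regression of pain score on arm, adjusted for the pre-block variables: age, BMI, prior surgery, adhesive disease, surgeon, route, type and planned concomitant procedures. Add adhesiolysis or excision performed in a sensitivity analysis only, because it is recorded after the block.

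Tabulate block use by surgeon before fitting. If individual surgeons nearly always or never use the block, the model has little within-surgeon contrast to work with, and the report should say so.

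The cost is a little abstraction time, some subjectivity in grading extent, and a few model degrees of freedom. Since the plan states no sample size, check the number of terms against the expected enrolment.

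### The 3-hour primary comparison has a mean difference but no test, model, interval or adjustment; with non-randomized block receipt, an unadjusted difference may mix block effect with case mix and surgeon

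*Combined protocol and SAP*

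**What the plan says.** The Data Collection Procedures section fixes the primary endpoint: "Our primary outcome is difference in pain scores at 3 hours". The Data Analysis paragraph is a single sentence. It names an effect measure, "the mean difference between pain scores at 1 hour, 3 hour, and 24 hour", and adds that "the difference in the amount of oral pain medication used will be assessed as below". What comes below is only the Expected Outcomes statement and the reference list.

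On allocation, the Design section says: "Based on surgeon's preference, and patient's consent, the patient is offered a QL block or not". Arms are then defined by whether the block was received. Data Collection Procedures confirms that "there will be no randomization or blinding done". Patients are those operated on "by attending physicians in the division of Minimally Invasive Gynecologic Surgery", so more than one surgeon is involved. Under Subjects, hysterectomy may be total or supracervical, by the laparoscopic or the robotic route.

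The plan will collect age, BMI, previous abdominal or pelvic operations, adhesive disease, operating time and PACU stay. It gives none of them a role in the analysis. Operating surgeon and procedure type are not named in that list.

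**The concern.** Study Objectives asks whether the block works as an analgesic adjunct, and Expected Outcomes hopes to show less pain with it. These are questions of effectiveness. In a cohort where preference decides treatment, a difference in means answers them only if the two groups are otherwise comparable, or are made so in the analysis.

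The Introduction itself describes obesity, previous surgery and adhesions as features of difficult patients, with longer operations and harder pain control. If such patients, or the patients of particular surgeons, are more or less likely to be blocked, an unadjusted 3-hour difference could hide a benefit or create one. Enrolling more patients would not remove that bias; it would make a biased result look more certain. Leaving test and adjustment open also allows them to be chosen after the scores are seen.

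**Working it through.** **Step 1. What is specified.** Effect measure: yes. Primary time point: yes. Test, model, interval, alpha, adjustment, matching or weighting, handling of surgeon: none anywhere in the document. No sample size, SD or expected effect is given either, so there is no figure of the plan's to reproduce. Everything below is illustration on assumed inputs.

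**Step 2. One unadjusted covariate.** Bias = (covariate effect on NRS) × (difference in prevalence between arms). Assumed: effect 1.0 to 1.5 points, prevalence difference 10 to 30 percentage points. Range: 1.0 × 0.10 = 0.10 to 1.5 × 0.30 = 0.45 points.

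With no true block effect and a two-sided 5% test, rejection = P(|Z + bias/SE| > 1.96), where SE = SD × √(2/n).

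| Bias, SD | 30 per arm | 50 per arm | 100 per arm |
|---|---|---|---|
| 0.10, 2.5 | SE 0.645: 5.3% | SE 0.500: 5.5% | SE 0.354: 5.9% |
| 0.45, 2.0 | SE 0.516: 14.0% | SE 0.400: 20.3% | SE 0.283: 35.6% |

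The first row is near nominal. If the bias runs against the block, power for a true 1.0-point benefit (SD 2.5, 50 per arm) falls from 51.6% to 43.7% (bias 0.10) or 19.6% (bias 0.45).

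**Step 3. Surgeon.** Assumed: four surgeons of equal volume, block rates evenly spaced from 30% to 70%, hard-case prevalence 35% to 65%, surgeon shift in pain −0.5 to +0.5 points, covariate effect 1.5, residual SD 2.5, no block effect.

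- Covariate imbalance = mean product of the deviations in block rate and prevalence, divided by 0.5 × 0.5. The deviations are ±0.20 and ±0.067 for block rate, ±0.15 and ±0.05 for prevalence. This gives 0.0167/0.25 = 0.067, about 7 points, worth 1.5 × 0.067 = 0.10 NRS points.
- The surgeon shift contributes, in the same way, 0.0556/0.25 = 0.22 points.
- If both point the same way, the bias is 0.10 + 0.22 = 0.32 (simulated 0.33). With the shift reversed it is 0.10 − 0.22 = −0.12 (simulated −0.12).

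Simulated rejection (10,000 runs), given as unadjusted / covariates only / covariates plus fixed surgeon:

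| Scenario | 50 per arm | 100 per arm |
|---|---|---|
| Same direction (false harm) | 9.0 / 5.8 / 4.0% | 13.4 / 8.5 / 4.4% |
| Its mirror image (false benefit) | 8.7 / 5.7 / 4.0% | 14.3 / 8.3 / 4.5% |
| Shift reversed | 5.5 / 5.9 / 3.7% | 6.2 / 8.3 / 4.2% |

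Covariates alone leave a bias of about 0.21 in size. In the reversed case they enlarge it, from −0.12 to −0.21. With the surgeon shift set to zero, unadjusted rejection is 5.0% and 5.7% at 50 and 100 per arm, so the inflation in this step depends on the assumed shift.

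**Step 4. Selection by difficulty within surgeon.** Add 0.10 to the block probability for hard cases and subtract 0.10 for others, in the same-direction scenario (imbalance 27 points; 6,000 runs). Rejection at 50 / 100 per arm is 22.9% / 40.4% unadjusted, 5.7% / 8.2% with covariates only, 8.0% / 11.9% with surgeon only, and 4.1% / 4.2% with both. The full model is given every confounder here; a real study would not have them all.

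**The case against.** The study is openly observational, and the Design section also states a descriptive aim: "Our aim is to follow the patient's pain scores post op and amount of oral pain medication used". That stands, but it does not dispose of the point, because the objective and the expected outcome are about effectiveness. An observational design makes control of confounding more necessary, not less.

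A reader might infer that the plan prescribes an unadjusted analysis. The text does not support this. It is silent on method and points to something below that is not there. The supplied text shows no redaction or missing figure at that place; loss in extraction is possible but unproven. What can be said is that the method is unspecified and could be unadjusted.

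A reader might also infer that the plan already collects most of what is needed for adjustment. That is not established: in Step 3 the larger part of the bias comes from surgeon, which the covariate list does not name. Nor does the list prove that surgeon or procedure type goes unrecorded, since its wording is inclusive rather than exhaustive.

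Finally, every input to the illustrations is assumed, and some settings give almost no inflation. The figures show what is possible, not what will happen.

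**Conclusion.** The point holds and should be settled before the data are analysed. It rests on two facts in the text: the primary comparison has no prespecified inference or adjustment, and block receipt follows preference without randomization. The simulations only illustrate.

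A reader might infer that confounding will flatter the block. The documents do not support that: the Introduction links case difficulty to pain, but nothing links it to the choice of block, so direction and size are both unknown. On the assumed inputs, false rejection at 50 per arm runs from near nominal (5.5%) to 20.3% for a single covariate. It reaches 22.9% when surgeon differences and selection within surgeon are combined. The listed covariates may not be enough without operating surgeon and planned procedure type.

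**What to change.** Replace the Data Analysis sentence with a full specification:

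- **Primary analysis.** Linear regression of 3-hour NRS on block receipt, adjusted for age, BMI, previous abdominal or pelvic surgery, endometriosis or adhesive disease, and planned procedure type, with a robust 95% CI and two-sided alpha 0.05. Use the same model at 1 and 24 hours.
- **Surgeon.** Record operating surgeon and planned procedure type. Include surgeon as a fixed effect when surgeons have both blocked and unblocked patients. A random intercept is less suitable, because it assumes surgeon effects are unrelated to block use.
- **Fallback.** If block use is all-or-none by surgeon, so that the coefficient cannot be estimated or rests on very few patients, report the covariate-adjusted model without surgeon and state that confounding by surgeon is unresolved. Fix in advance what counts as very few, using block counts only.
- **Oral medication.** Convert to one common unit and use the same adjusted linear model with a robust CI.
- **Supportive.** Report the unadjusted difference, a covariate balance table and the block rate by surgeon.
- **Variables arising after the block.** The Design section places the block before surgery: "The QL block will be in the operating room after induction prior to starting the scheduled surgical procedure". PACU stay should therefore not be adjusted for, and operating time belongs only in a sensitivity analysis.
- **Conclusion.** Word it as an adjusted association with residual confounding possible, including by preoperative pain, which is not among the listed data.

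The cost is analysis wording, a little code and two fields, with no extra visits. The conclusion becomes more cautious and the interval wider. On the Step 3 inputs, the mean SE of the full model compared with the unadjusted one at 30 / 50 / 100 per arm rises by:

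| Block rates across surgeons | SE increase |
|---|---|
| No selection | 14% / 5% / 1% |
| 30% to 70% | 18% / 9% / 3% |
| 10% to 90% | 43% / 31% / 24% |

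In the last row, holding precision would take about 1.24² = 1.5 to 1.43² = 2.0 times the patients. At 50 per arm (SE 0.534 to 0.702), approximate power for a 1.0-point benefit falls from 46% to 30%. Where surgeons differ that strongly in block use, this loss should be stated openly.

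### As written, the 24-hour pain comparison would rest on patients who answer the telephone call and would not use their 1- and 3-hour scores; it is biased if non-response relates to early pain differently in the two arms

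*Combined protocol and SAP*

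**What the plan says.** All references are to the combined protocol and SAP.

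- **Outcomes** (under Data Collection Procedures): "Our primary outcome is difference in pain scores at 3 hours". Then: "Our secondary outcome is difference in pain scores, at 1 hour, 24 hours", followed by oral medication and adverse effects.
- **Analysis** (Data Analysis): the plan for pain is "the mean difference between pain scores at 1 hour, 3 hour, and 24 hour". The sentence then turns to medication and closes by pointing forward to a method: "the difference in the amount of oral pain medication used will be assessed as below". What comes next is Expected Outcomes and then References. No test, model, covariate adjustment, imputation or missing-data rule appears anywhere.
- **Early scores** (Data Collection Procedures): after transfer to the PACU, "Pain levels will be documented at the same 1- and 3-hours intervals" as the medication records.
- **24-hour score** (Data Collection Procedures): "Study subjects will receive a telephone call 24 hours after surgery and asked about how much additional medication they have taken for pain control", and the same call asks for the pain level. No calling window, call-back rule or expected response rate is given.
- **Arms** (Design; Data Collection Procedures): "Based on surgeon's preference, and patient's consent, the patient is offered a QL block or not", and "there will be no randomization or blinding done".

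**The concern.** The early scores do not depend on the patient being reached after discharge from the PACU; the 24-hour score does. Some patients will probably not answer. A mean difference at 24 hours with no missing-data rule can then be formed only from those who do, so the 24-hour comparison may describe a different set of patients from the 3-hour comparison.

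That matters if answering is related to pain and the relation differs between arms. Surgeon and patient choose the block and everyone knows who had it, so nothing in the design makes response alike in the two arms. The 1- and 3-hour scores carry information about the missing 24-hour scores, and a separate difference at each time does not use it. At stake is a named secondary outcome, the only pain score after 3 hours.

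**Working it through.** **Inputs.** From the documents: the three time points, the source of each score, the 1-10 scale, and the lack of randomisation and blinding. They give no SD, correlation, response rate, effect size or sample size, so there is no planned figure to reproduce. Everything below is assumed: normal scores, SD 2.5, correlations 0.6 (1 h with 3 h), 0.5 (3 h with 24 h) and 0.4 (1 h with 24 h), and a true 24-hour difference of 0. The log-odds of non-response rise by 0.7 per SD of 3-hour pain.

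**1. Bias of the responder-only mean.** Let z be the standardised 3-hour score and p(z) the chance of non-response, with logit p(z) = a + 0.7z and a chosen to give overall non-response m. The mean z among responders is d = ∫ z(1 − p(z))φ(z)dz / (1 − m). In an arm where non-response depends on early pain, the 24-hour responder mean is off by r × SD × d = 0.5 × 2.5 × d = 1.25d. An arm with random non-response contributes 0, whatever its rate. If the patterns run in opposite directions, the two errors add.

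| m | a | d | One arm only (size of 1.25d) | Opposite directions (doubled) |
|---|---|---|---|---|
| 10% | −2.385 | −0.0668 | 0.08 | 0.17 |
| 20% | −1.523 | −0.1299 | 0.16 | 0.32 |
| 30% | −0.937 | −0.1915 | 0.24 | 0.48 |

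These values come from numerical integration. Simulation agrees to within about 0.01, giving 0.08 to 0.09 at 10%. The sign depends on which arm loses its patients with more pain: if it is the control arm, the benefit of the block is understated; if it is the block arm, it is overstated.

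**2. Same rule in both arms.** The errors cancel and the bias is about 0. In a separate simulation (SD 2) where the arms differ by 1 point at 3 hours, a common rule leaves only about 0.01 to 0.07.

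**3. Other assumptions.** With SD 2, equal correlations of 0.3 to 0.7, non-response of 10% to 30% and a slope of 0.4 per point, the bias is 0.04 to 0.30 for dependence in one arm and 0.09 to 0.60 for opposite directions. At 20% non-response and correlation 0.5 it is about 0.15 and 0.29.

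**4. Using the early scores.** Predicting the 24-hour score from the 1- and 3-hour scores brings the bias to about 0 in all these scenarios (largest absolute value 0.017, which is simulation error). This is expected, because non-response was made to depend only on the 3-hour score.

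**5. Non-response driven by 24-hour pain.** With the step 1 assumptions, 20% non-response and dependence in one arm, the raw bias is 2.5 × 0.1299 = 0.32 and the modelled bias is 0.24. The share remaining is 0.24 / 0.32 = 0.75. With opposite directions the figures are about 0.65 raw and 0.48 modelled.

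**6. Precision under random non-response.** With equal correlation r, the variance of the 24-hour mean is multiplied by 1 − mR², where R² = 2r²/(1 + r).

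- r = 0.3, m = 0.1: R² = 0.18/1.3 = 0.138, and 1 − 0.0138 = 0.986, a 1% reduction.
- r = 0.7, m = 0.3: R² = 0.98/1.7 = 0.576, and 1 − 0.173 = 0.827, a 17% reduction.

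**The case against.** **The plan does not choose a responder-only analysis.** A reader might infer that it does. The documents do not say so: a mean difference names what will be reported, the promised method is absent, and a mixed model would report the same three differences as contrasts. This stands. The responder-only comparison is what results if nothing is added, and the more basic gap is that no method is stated.

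**The size is assumed and modest.** This stands too. At 20% non-response in one arm, 0.16 points is 0.16 / 2.5 = 0.06 SD. With an assumed 50 patients per arm and 20% missing, the standard error of the 24-hour difference is 2.5 × √(2/40) = 0.56. The figures of 0.32 to 0.48 need opposite patterns in the two arms, and nothing in the documents suggests a mechanism for that.

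**The model is not a full cure.** If patients fail to answer because of their pain at 24 hours, about three quarters of the bias remains. Nor is its assumption strictly weaker than that of the raw difference, which also holds when non-response acts alike in both arms, including through 24-hour pain. In one such case, with an assumed halved early-to-late correlation under block, the raw bias was about 0 and the modelled bias −0.05 to −0.09. This stands and limits what the fix can claim.

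**Other matters weigh more.** The choice of block by surgeon and patient threatens every comparison, and early scores do not remove that. This is correct, but it is no reason to leave 24-hour non-response unaddressed when handling it needs only wording.

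**Conclusion.** The point holds as a conditional weakness in a secondary analysis. Followed as written, the plan gives a 24-hour comparison of responders only that does not use their earlier scores. It is biased if non-response relates to early pain differently by arm and early pain predicts 24-hour pain. Under the SD of 2.5 and correlation of 0.5 assumed above, the bias is about 0.08 to 0.24 points for dependence in one arm, and about 0 under a common rule. None of these values comes from the documents.

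Three stronger readings are not supported. The documents do not show that the 24-hour result will be biased, because they say nothing about response. The primary result is not undermined, because the 3-hour score does not depend on the call. And the 24-hour pain score is not the only evidence of lasting benefit, because the same call records medication use.

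The change is worth making because it uses data already collected and improves precision even when non-response is random.

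**What to change.** Replace the three separate differences with one repeated-measures linear mixed model of the 1-, 3- and 24-hour scores:

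- Include arm, time, arm-by-time and the preoperative covariates already listed (age, body mass index, surgical history, history of adhesive disease), with unstructured covariance and every patient who has at least one score.
- Read the 3-hour contrast as primary and the 1- and 24-hour contrasts as secondary.
- Report response to the 24-hour call by arm and by 3-hour pain.
- Keep the responder-only difference as a sensitivity analysis, and add one for non-response that depends on the unseen 24-hour pain.
- State separately how non-response is handled for the 24-hour medication outcome, which this model does not cover.

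The cost is analysis wording, with no new data or visits. The downside is a somewhat more complex model that assumes non-response is explained by arm, early scores and covariates, which is a different assumption from that of the raw difference. Confounding by choice of block is addressed only as far as the covariates allow.
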